		Alarming: The 95% confidence interval of the between-group difference in absolute mRS 4–6 rate does not include 0.0	Notion on safety concern added to the conclusion.	Group A/B was associated with an alarmingly higher rate of unfavorable functional outcome. Given the event rate, the confidence in this finding was moderate .
>15%	High	Concerning: The 85% confidence interval of the between-group difference in absolute mRS 4–6 rate does not include 0.0	Notion on safety concern added to the conclusion.	Group A/B was associated with a concerningly higher rate of unfavorable functional outcome. Given the event rate, the confidence in this finding was high .
		Alarming: The 95% confidence interval of the between-group difference in absolute mRS 4–6 rate does not include 0.0	Notion on safety concern added to the conclusion.	Group A/B was associated with an alarmingly higher rate of unfavorable functional outcome. Given the event rate, the confidence in this finding was high .

Table 5. Safety concerns for the intention-to-treat dataset.

Variable	All patients (n=??)	Group A (n=??)	Group B (n=??)	Difference (95% CI)	Difference (85% CI)	P-value
6 mo mortality	??/n (??%)	??/n (??%)	??/n (??%)	x (x to x)	x (x to x)	??
6 mo mRS 4–6	??/n (??%)	??/n (??%)	??/n (??%)	x (x to x)	x (x to x)	??

Abbreviations: mRS=modified Ranking Scale, CI=confidence interval

Table 6. Safety concerns for the per-protocol dataset.

Variable	All patients (n=??)	Group A (n=??)	Group B (n=??)	Difference (95% CI)	Difference (85% CI)	P-value
6 mo mortality	??/n (??%)	??/n (??%)	??/n (??%)	x (x to x)	x (x to x)	??
6 mo mRS 4–6	??/n (??%)	??/n (??%)	??/n (??%)	x (x to x)	x (x to x)	??

Abbreviations: mRS=modified Ranking Scale, CI=confidence interval

Imbalance in the incidence of safety concerns (mortality and/or mRS 4–6)?

NO / YES [INCORRECT OPTION TO BE REMOVED]

If NO, the following sentence will be added to the conclusion: “There were no relevant differences in mortality or functional outcome between the groups.”

If YES, interpretation according to **Table 3** (mortality) and **Table 4** (unfavorable functional outcome)

Step 4: Unblinding of treatment groups

Having now considered both the rate of reoperations and safety concerns, we have now reached a consensus on our blinded assessment of efficacy.

Our statistician will now unblind the treatment group assignment (break the randomization code):

- Group A = Irrigation / No irrigation [**INCORRECT OPTION TO BE REMOVED**]
- Group B = Irrigation / No irrigation [**INCORRECT OPTION TO BE REMOVED**]

Given the above noted, the FINISH data is shown in **Table 1**, **Table 2**, **Table 5 and Table 6** (with n-values for Groups to be added) and in Scenario 1 (**Figure 2**) or Scenario 2 (**Figure 3**). [**INCORRECT OPTION TO BE REMOVED**]. The rate of crossovers is reported here:

- Crossovers from Group A to B, n=?? [**INSERT DATA**]
- Crossovers from Group B to A, n=?? [**INSERT DATA**]

[**COPY TABLE 1 HERE AND INSERT DATA**]

[**COPY TABLE 2 HERE AND INSERT DATA**]

[**COPY TABLE 5 HERE AND INSERT DATA**]

[**COPY TABLE 6 HERE AND INSERT DATA**]

[**COPY FIGURE 2 OR FIGURE 3 HERE**]

Step 5: Unblinded interpretation of treatment effect

Accordingly, our penultimate interpretation of the FINISH trial is as follows:

[CORRECT OPTION TO BE CHOSEN]

Treatment comparison	Primary outcome results	Interpretation based on primary outcome	Between-group difference in safety concerns (mortality, mRS 4-6)	Interpretation commitment regarding safety concerns (mortality, mRS 4-6)
No intraoperative irrigation vs. intraoperative irrigation	Non-inferior	Among adults with symptomatic chronic subdural hematoma who had undergone burr-hole drainage, no intraoperative irrigation was noninferior to intraoperative irrigation in preventing reoperations.	No difference	There were no relevant differences in mortality or functional outcome between the groups.
			Difference	“Interpretation commitment” from Tables 3 and 4 added if criteria for addition to conclusion is fulfilled.
	Superior	Among adults with symptomatic chronic subdural hematoma who had undergone burr-hole drainage, no intraoperative irrigation was superior to intraoperative irrigation in preventing reoperations. However, be it noted that we did not design the study to show superiority.	No difference	There were no relevant differences in mortality or functional outcome between the groups.
			Difference	“Interpretation commitment” from Tables 3 and 4 added if criteria for addition to conclusion is fulfilled.
	Inferior	Among adults with symptomatic chronic subdural hematoma who had undergone burr-hole drainage, no intraoperative irrigation was inferior to intraoperative irrigation in preventing reoperations. However, be it noted that we did not design the study to show inferiority.	No difference	There were no relevant differences in mortality or functional outcome between the groups.
			Difference	“Interpretation commitment” from Tables 3 and 4 added if criteria for addition to conclusion is fulfilled.
	Inconclusive	Among adults with symptomatic chronic subdural hematoma who had undergone burr-hole drainage, the effect of intraoperative irrigation compared to no intraoperative irrigation in preventing reoperations was inconclusive .	No difference	There were no relevant differences in mortality or functional outcome between the groups.
			Difference	“Interpretation commitment” from Tables 3 and 4 added if criteria for addition to conclusion is fulfilled.

Step 6: Final interpretation

Our final interpretation of the FINISH trial stands as follows:

[COPY PASTE THE CORRECT INTERPRETATION HERE FROM STEP 5]

Place: [ZOOM-/Teams-meeting]
Time: [Insert date here]

[name]
(BDI committee chair)

[name]
(BDI committee co-chair)

[name]
(trial statistician)

[name]
(BDI committee member)

[name], member
(BDI committee member)

Also present at the meeting:

4. References

1. Tommiska P, [name] R, Schwartz C, Kivisaari R, Luostarinen T, Satopää J, et al. Finnish study of intraoperative irrigation versus drain alone after evacuation of chronic subdural haematoma (FINISH): a study protocol for a multicentre randomised controlled trial. *BMJ Open* [Internet]. 2020 [cited 2020 Aug 21];10. Available from: <https://www.ncbi.nlm.nih.gov/pmc/articles/PMC7311024/>
4. van Swieten JC, Koudstaal PJ, Visser MC, Schouten HJ, van Gijn J. Interobserver agreement for the assessment of handicap in stroke patients. *Stroke*. 1988;19:604–7.

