2.9 Sample size

2.9.1 Original sample size calculation

The original sample size calculation was presented in the protocol as follows [1]:

The trial is designed to ascertain whether drain without irrigation is non-inferior to drain with irrigation, with the rate of reoperations of ipsilateral CSDHs within 6 months as the primary outcome. We based the standard rate of reoperations (9.6%) on the results from a recent Cochrane review that reported the recurrence rates after CSDH evacuation followed by subdural drainage in six randomized controlled trials (RCTs) with more than 30 patients per treatment arm [5]. This yielded a maximum allowed margin of 9.0% to achieve non-inferiority. Following a consensus meeting with the trial investigators, the non-inferiority margin was lowered to 7.5%. Thus, with a non-inferiority margin of 7.5%, a 2.5% level of statistical significance (alpha=0.025) and an 80% power (beta=0.20), we will need 243 patients per study group [6]. Accounting for a drop-out rate of 10%, the required group size increases to 270 per study group. Accordingly, we set the recruitment target at 540 patients.

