Summary statistics will be presented for both groups. Continuous variables will be presented in terms of mean values or medians with SDs and IQRs, respectively. Categorical variables will be presented with relative frequencies in percent.

The results from the statistical analysis will be considered to support a claim of non-inferiority if the upper limit of a one-sided 97.5% CI (or equivalently a 95% two-sided CI) excludes a difference in the primary endpoint in favor of the irrigation group of more than 7.5%. The center stratification of the randomization will be accounted for in the calculation of the CI.

Exploratory analyses of secondary and other binary endpoints will be performed using the χ^2 test or logistic regression analysis. Continuous outcomes will be analyzed using regression Student's t-test, analysis of covariance or regression models.

Potential effect modifiers will be analyzed by including interaction terms in statistical models for the following subgroups:

- patient age (<70 years, \geq 70 years)
- GCS score at baseline (9–12, 13–14, 15)
- history of head trauma (<4 weeks, \geq 4 weeks, head trauma with unknown timing, no head trauma)
- unilateral versus bilateral CSDH
- use of anticoagulation and/or antiplatelet medication versus none
- preoperative mRS (0–3, 4–5)
- hematoma density (isodense, mixed-density, hypodense)
- hematoma size (width in mm)
- presence of membranes on preoperative imaging (yes, no)

The primary endpoint will be investigated as described above using a CI, which is equivalent to using a non-inferiority test with a one-sided p-value of 0.025 (or a two-sided of 0.05). The between-group comparison of 6-month mortality and mRS 4–6 differences will be compared using 85% and 95% CIs (as outlined in more detail in the BDI). The statistical testing of other endpoints will also be performed using a two-sided significance level of 0.05.

STATA (Statistics/Data analysis, SE v15.1, StataCorp LLC, [name]) will be used for analyses.

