 [name] (Jun 27, 2023 07:13 GMT+3) [name] (SCM, trial PI)

 Jun 27, 2023
 [name] (Jun 27, 2023 23:06 GMT+3) [name] (SCM, BDI committee co-chair)

[figure not shown]
 Jun 27, 2023
 [name] (Jun 27, 2023 10:56 GMT+3) [name] (SCM, BDI committee chair)

*SCM = Steering Committee Member of the FINISH trial

4. Blinded data interpretation (BDI)

The data will be interpreted according to a blinded data interpretation scheme we have published and described in detail previously [9]. In brief, the FINISH statistician (TC) will carry out the statistical analyses, blinded to the group assignment, and presents the data as Group A and Group B. The FINISH Blinded Data Interpretation committee will then contemplate the blinded results until a consensus on the interpretation is reached. Once the Blinded Data Interpretation committee reaches a consensus, the data will be unblinded and no changes are made to the interpretation of the results.

The sequence of events to take place in the upcoming ‘blinded data interpretation meeting’ is outlined in the flow chart below:

The final BDI plan was approved by:

Jun 27, 2023
[name] (Jun 27, 2023 07:13 GMT+3)
[name] (trial PI)

Jun 27, 2023
[name] (Jun 27, 2023 00:01 GMT+3)
[name] (local PI, SCM)

Jun 27, 2023
[name] (Jun 27, 2023 08:43 GMT+3)
[name] (local PI, SCM)

Jun 28, 2023
[name] (Jun 28, 2023 15:02 GMT+3)
[name] (local PI, SCM)

Jun 27, 2023
[name] (Jun 27, 2023 08:33 GMT+3)
[name] (local PI, SCM)

Jun 27, 2023
[name] (Jun 27, 2023 08:21 GMT+3)
[name] (local PI, SCM)

Jun 27, 2023
[name] (Jun 27, 2023 14:13 GMT+3)
[name] (SCM)

Jun 27, 2023
[name] (Jun 27, 2023 07:55 GMT+3)
[name] (SCM)

Jun 28, 2023
[name] (Jun 28, 2023 10:49 GMT+2)
[name] (trial statistician)

Jun 27, 2023
[name] (Jun 27, 2023 18:40 GMT+2)
[name] (BDI committee member)

Jun 27, 2023
[name] (Jun 27, 2023 09:55 GMT+3)
[name] (SCM, BDI committee member)

Jun 27, 2023
[name] (Jun 27, 2023 23:06 GMT+3)
[name] (SCM, BDI committee co-chair)

Jun 27, 2023
[name] (Jun 27, 2023 10:56 GMT+3)
[name] (SCM, BDI committee chair)

*SCM = Steering Committee Member of the FINISH trial

Minutes of the BDI**[BLINDED VALUES TO BE ADDED BY TRIAL STATISTICIAN PRIOR TO THE BDI MEETING]****Step 1: Analysis of efficacy (primary, non-inferiority analysis)**

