Is no intraoperative irrigation non-inferior to irrigation in preventing symptomatic CSDH recurrence that requires reoperation after burr-hole craniostomy and subdural drainage in patients with CSDH? Based on the data in Table 2 and Figures 2 and 3, we will make an initial (blinded) interpretation on efficacy. Table 1 below describes the baseline characteristics of the study population.

Table 1. Baseline characteristics of the participants randomly assigned to irrigation or no irrigation.

Characteristic	Group A (n=??)	Group B (n=??)
Age – yr		
Female sex – no./total no. (%)		
Medical comorbidities – no./total no. (%)		
Diabetes mellitus		
Cardiac arrhythmia		
Previous cerebrovascular event		
Hypertension		
Ischemic heart disease or peripheral artery disease		
Cardiac valve prosthesis		
Pulmonary embolism or deep vein thrombosis*		
Dementia		
History of head trauma – no./total no. (%)		
Yes		
No		
Unknown		
Preoperative use of antithrombotic medication – no./total no. (%)		
No		
Antiplatelet		
Anticoagulant		
Symptoms at admission – no./total no. (%)		
Gait disturbance or falls		
Hemiparesis		
Speech disturbance		
Cognitive impairment		
Headache		
Seizure		
Other		
GCS at admission – no./total no. (%)		
15		
13–14		
9–12		
mRS at admission – no./total no. (%)		
1–3		
4–5		
Midline shift – mm		
Hematoma laterality† – no./total no. (%)		
Unilateral		
Bilateral		
Hematoma width, mm – mean (sd)		
Unilateral		
Bilateral‡		
Hematoma density§ – no./total no. (%)		
Isodense		
Hypodense		
Mixed density		
Hematoma membranes§ – no./total no. (%)		
Yes		
No		

* within 12-months before admission

† patient may have a hematoma not operated on

‡ sum of left and right hematoma widths

§ presented as individual hematomas

Abbreviations: GCS=Glasgow Coma Scale, mRS=modified Rankin Scale, SD=Standard Deviation, yr=years

[figure not shown]
Figure 1. Trial flow chart.

Table 2. Primary outcome at the primary outcome assessment time point (6 months).

Variable	Group A	Group B	Difference (97.5% CI)	P-value
Intention-to-treat				
Secondary surgery for recurrent CSDH	n=?? ??/n (x%)	n=?? ??/n (??%)	x (x to x)	??
Per-protocol-treated				
Secondary surgery for recurrent CSDH	n=?? ??/n (x%)	n=?? ??/n (??%)	x (x to x)	??

Abbreviations: CSDH=chronic subdural hematoma, CI=confidence interval

Our judgment on the efficacy (non-inferiority) will be based on the location of the whole CI in relation to Δ (non-inferiority margin) [10].

[figure not shown]

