As we will not have knowledge of treatment group assignment (whether Group A or Group B is our “new treatment”, here, no irrigation), and to preserve our blinding, we have deemed it necessary to take both scenarios under consideration, as follows:

[figure not shown]
- We will calculate the treatment group difference assuming first that Group A is the “new treatment” and then that Group B is the “new treatment” (Scenario 1 and Scenario 2).
- We will plot the resulting point estimate with confidence intervals (97.5% CIs) into two separate graphs.
- We will interpret both graphs (Figures 2 and 3).

Figure 2. Scenario 1 – Group A minus Group B.

[EXAMPLE GRAPH BELOW, to be replaced by the actual graph of the FINISH trial data]

**Figure 3.** Scenario 2 – Group B minus Group A.

[EXAMPLE GRAPH BELOW, to be replaced by the actual graph of the FINISH trial data]

Step 2: Initial interpretation of efficacy

Based on the location of the whole CI in relation to Δ (non-inferiority margin), our initial interpretation on the non-inferiority of no irrigation vs. irrigation, is as follows:

Scenario 1 (Figure 2) [INCORRECT OPTION TO BE REMOVED]

1. Among adults with symptomatic chronic subdural hematoma who had undergone burr-hole drainage, Group A was [superior A / non-inferior B, C, D / inferior H] to Group B in preventing reoperations.

OR

2. Among adults with symptomatic chronic subdural hematoma who had undergone burr-hole drainage, the effect of Group A compared to Group B in preventing reoperations was inconclusive [E, F, G].

Scenario 2 (Figure 3) [INCORRECT OPTION TO BE REMOVED]

3. Among adults with symptomatic chronic subdural hematoma who had undergone burr-hole drainage, Group B was [superior A / non-inferior B, C, D / inferior H] to Group A in preventing reoperations.

OR

4. Among adults with symptomatic chronic subdural hematoma who had undergone burr-hole drainage, the effect of Group A compared to Group B in preventing reoperations was inconclusive [E, F, G].

Step 3: Analysis of safety concerns

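### The primary-outcome interval in the BDI template is labelled 97.5% with two limits, while section 3.2 decides non-inferiority on a one-sided 97.5% (two-sided 95%) limit

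*SAP*

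**What the plan says.** Section 3.2 (Final statistical analysis plan) supports non-inferiority when the "upper limit of a one-sided 97.5% CI (or equivalently a 95% two-sided CI" rules out a difference of more than 7.5 percentage points in favour of irrigation. It restates this as a test with a "one-sided p-value of 0.025 (or a two-sided of 0.05". The sample size in section 2.9.1 uses the same level: "2.5% level of statistical significance (alpha=0.025".

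The BDI template in section 4 is worded differently. In Step 1, the results column of Table 2 is headed "Difference (97.5% CI", and each cell takes a point estimate with two limits. For Figures 2 and 3 the instruction is: "We will plot the resulting point estimate with confidence intervals (97.5% CIs) into two separate graphs". The efficacy judgement "will be based on the location of the whole CI" relative to the margin, and Step 2 sorts the result into superior, non-inferior, inferior or inconclusive. The visible text of Steps 1 and 2 does not call the interval one-sided.

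Tables 5 and 6 of the same template use the same cell format under "Difference (95% CI" and under an 85% heading. Those are ordinary two-sided intervals, judged on whether they contain zero.

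Section 4 also fixes the outcome of the meeting: once the committee agrees, "the data will be unblinded and no changes are made to the interpretation of the results".

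**The concern.** A one-sided 97.5% interval has one finite limit. Table 2 and the figures need two, and the superior and inferior categories use both. The label therefore has two possible meanings:

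- **A two-sided 97.5% CI.** Each tail holds 1.25%, and the template contradicts section 3.2 and the sample-size alpha.
- **A two-sided 95% CI**, with the one-sided level printed over it. The decision is as planned, but the primary-outcome table carries the wrong confidence level.

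Read by the convention of Tables 5 and 6, it is the first. Nothing in the template settles it.

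The committee reads its conclusion from this interval and cannot revise it after unblinding. If the interval is computed as labelled, a result that satisfies section 3.2 can be declared inconclusive, and the boundaries for superior and inferior also move. If the question is noticed only once results are on the table, the level is chosen with the data in view. The data are blinded, but the scheme exists to prevent such choices.

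**Working it through.** **Inputs from the SAP.** Reoperation rate 9.6%, taken as equal in both arms; margin 7.5 points; alpha 0.025; power 80%; 243 per group (section 2.9.1). Non-adherence 15.7%; recalculated total 578, or 289 per group (section 2.9.2).

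**The plan's own figure.** n per group = (1.960 + 0.842)² × 2 × 0.096 × 0.904 / 0.075² = 242.2, rounded up to 243. This reproduces the SAP and confirms that the design uses z = 1.960.

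**Effect of the label.** A two-sided 95% CI uses z = 1.960. A two-sided 97.5% CI uses z = 2.241. The ratio is 2.241 / 1.960 = 1.14, so the interval is 14% wider, and one-sided alpha is 0.025 / 2 = 0.0125.

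**Power.** Power = Φ(0.075 / SE − z), with SE = √(2p(1 − p)/n). The per-protocol size is 578 × (1 − 0.157) / 2 = 243.6 per group; the intention-to-treat (ITT) size is 289 per group.

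At p = 9.6%:

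- Per-protocol: SE = 0.02669 and 0.075 / SE = 2.810. Φ(2.810 − 1.960) = 80.2%; Φ(2.810 − 2.241) = 71.5%.
- ITT: SE = 0.02451 and 0.075 / SE = 3.060. Φ(3.060 − 1.960) = 86.4%; Φ(3.060 − 2.241) = 79.4%.

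Section 3.2 requires both analyses to succeed. The last column gives that joint power by simulation (400,000 runs, 244 per-protocol patients nested in 289 per arm, same event rate). The 6% and 12% rates are assumptions, included to show the range. Each cell shows z = 1.960, then z = 2.241.

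| True rate, both arms | Per-protocol | ITT | Both |
|---|---|---|---|
| 6% | 93.6% → 89.3% | 96.7% → 94.0% | 92.8% → 88.7% |
| 9.6% | 80.2% → 71.5% | 86.4% → 79.4% | 78.7% → 69.7% |
| 12% | 72.2% → 62.0% | 79.2% → 70.3% | 70.1% → 59.8% |

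Using the 587 randomised (section 2.2), the per-protocol size is 587 × 0.843 / 2 = 247.4 per group, and power at 9.6% falls from 80.8% to 72.2%. Restoring 80% at alpha 0.0125 would take 294 evaluable patients per group instead of 243.

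**Observed results that change category.** The largest observed difference that still passes is 7.5 − z × 100 × SE. At 289 per arm, the results that meet section 3.2 but read as inconclusive under the label are:

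- at 6%: about 3.1 to 3.6 points
- at 9.6%: about 2.0 to 2.7 points
- at 12%: about 1.4 to 2.2 points

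**Worked example** (unstratified Wald interval): 36 of 289 without irrigation against 30 of 289 with it. The difference is 12.46% − 10.38% = 2.08 points, with SE 2.644 points.

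- Upper limit with z = 1.960: 2.08 + 5.18 = 7.26, below the margin, so non-inferior.
- Upper limit with z = 2.241: 2.08 + 5.93 = 8.00 (from unrounded values), above the margin, so inconclusive.

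**Superior and inferior calls.** At 289 per arm and 9.6%, the observed difference needed to exclude zero moves from 1.960 × 2.451 = 4.8 points to 2.241 × 2.451 = 5.5 points.

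**Type I error.** By exact binomial enumeration at the margin (17.1% v 9.6%, 289 per arm, unpooled Wald), it is 2.65% with z = 1.960 and 1.35% with z = 2.241.

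**The case against.** The strongest reply is that the decision level is not in doubt. Section 3.2 states it twice, the sample size agrees, and the table of SAP changes in section 3.3 announces no stricter level. Wherever else the SAP writes 97.5%, it means the one-sided level. The trial statistician approved both the SAP and the BDI plan and will fill in Table 2. The two limits also have an innocent explanation: the template reports A minus B and B minus A because the arms are masked, and each limit is then the one-sided 97.5% limit for one of the two scenarios. Finally, the schematic and example graphs are not available here and may state the level.

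Much of this stands. Shorthand is the more likely reading, and under it no power is lost. Section 3.2 is clear, and the remark about missing figures limits the finding to the visible text.

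It does not rescue the label. An interval whose two ends are each one-sided 97.5% limits is a two-sided 95% CI and should be labelled so. The clarity of section 3.2 makes the template inconsistent with it; it does not correct the template, and the template is what the committee interprets. The table and the bullet remain wrong as written, whatever the figures show.

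**Conclusion.** The point holds and should be fixed. The label on the primary-outcome interval disagrees with section 3.2 under either reading, and that interval produces the locked conclusion.

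The size depends on what was meant. If 97.5% is shorthand, the harm is a wrong confidence level in Table 2 and Figures 2 and 3, with no effect on alpha or power. If it is computed as labelled, about 9 points of per-protocol power are lost at the planning rate (80.2 − 71.5 = 8.7), and section 2.9.2 enlarged the trial specifically to protect that analysis. The direction is conservative: type I error is not inflated, and no false non-inferiority claim can result.

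The power figures assume equal true rates, a normal approximation, the planned 289 per arm with 15.7% lost to the per-protocol set, and no centre stratification. Confidence is high for the mismatch itself; the power loss is conditional on the literal reading.

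**What to change.** Before the BDI meeting, replace the 97.5% label in the Table 2 column and in the Step 1 bullet for Figures 2 and 3 with: two-sided 95% CI (upper limit = one-sided 97.5% limit), computed with the centre stratification that section 3.2 requires. State that every superior, non-inferior, inferior and inconclusive call in Step 2 is made from that interval, and check that the schematic and example graphs carry the same level.

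This changes one table heading and one bullet. It leaves the section 3.2 criterion, the margin and the sample size as they are. Because the plan is signed, the correction needs a short, dated revision recorded before the results are seen.

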Acknowledging that the FINISH trial was not powered for assessing differences in mortality or rate of unfavorable functional outcome (mRS 4–6), we used a 3-level hierarchy (**low** / **moderate** / **high**) for expressing our confidence in the possible between-group differences according to the GRADE approach [14–16]. We assumed a 6-month mortality rate of 5% [12,17] and an mRS 4–6 rate of 10% [12]. In terms of **mortality**, the confidence in the estimate was considered **low** if the overall 6-month mortality rate was **<5%**, **moderate** if the overall 6-month mortality rate was **5–10%**, and **high** if the overall 6-month mortality rate was **>10%**. Regarding 6-month unfavorable functional outcome (**mRS 4–6**), the confidence in the estimate was considered **low** if the rate of mRS 4–6 was **<10%**, **moderate** if the rate of mRS 4–6 was **10–15%**, and **high** if the rate of mRS 4–6 was **>15%**.

Our scheme for interpreting the possible safety concerns is outlined in Tables 3 and 4.

Table 3. A priori set thresholds for **concerning** and **alarming** between-group differences in 6-month mortality with associated confidence estimates and pre-determined commitments for interpretation.

Overall mortality in whole population	Confidence in estimate	Threshold for relevant between-group difference in mortality	Resulting action if threshold fulfilled	Authors' interpretation commitment
<5%	Low	Concerning: The 85% confidence interval of the between-group difference in absolute mortality-% does not include 0.0	None	We refrain from making any comments due to the low event rate (low confidence in effect estimate).
		Alarming: The 95% confidence interval of the between-group difference in absolute mortality-% does not include 0.0	Notion on safety concern added to the discussion (not added to the conclusion).	Group A/B was associated with an alarmingly higher mortality rate. Given the event rate, the confidence in this finding was low .
5–10%	Moderate	Concerning: The 85% confidence interval of the between-group difference in absolute mortality-% does not include 0.0	Notion on safety concern added to the discussion (not added to the conclusion).	Group A/B was associated with a concerningly higher mortality rate. Given the event rate, the confidence in this finding was moderate .

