		Alarming: The 95% confidence interval of the between-group difference in absolute mortality-% does not include 0.0	Notion on safety concern added to the conclusion.	Group A/B was associated with an alarmingly higher mortality rate. Given the event rate, the confidence in this finding was moderate .
>10%	High	Concerning: The 85% confidence interval of the between-group difference in absolute mortality-% does not include 0.0	Notion on safety concern added to the conclusion.	Group A/B was associated with a concerningly higher mortality rate. Given the event rate, the confidence in this finding was high .
		Alarming: The 95% confidence interval of the between-group difference in absolute mortality-% does not include 0.0	Notion on safety concern added to the conclusion.	Group A/B was associated with an alarmingly higher mortality rate. Given the event rate, the confidence in this finding was high .

Table 4: A priori set thresholds for concerning and alarming between-group differences in 6-month mRS4–6 with associated confidence estimates and pre-determined commitments for interpretation

Overall mRS 4–6 in whole population	Confidence in estimate	Threshold for relevant between-group difference in mRS 4–6	Resulting action if threshold fulfilled	Authors' interpretation commitment
<10%	Low	Concerning: The 85% confidence interval of the between-group difference in absolute mRS 4–6 rate does not include 0.0	None	We refrain from making any comments due to the low event rate (low confidence in effect estimate).
		Alarming: The 95% confidence interval of the between-group difference in absolute mRS 4–6 rate does not include 0.0	Notion on safety concern added to the discussion (not added to the conclusion).	Group A/B was associated with an alarmingly higher rate of unfavorable functional outcome. Given the event rate, the confidence in this finding was low .
10-15%	Moderate	Concerning: The 85% confidence interval of the between-group difference in absolute mRS 4–6 rate does not include 0.0	Notion on safety concern added to the discussion (not added to the conclusion).	Group A/B was associated with a concerningly higher rate of unfavorable functional outcome. Given the event rate, the confidence in this finding was moderate .

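### In the top event-rate bands of Tables 3 and 4, a difference whose 95% CI still includes zero goes into the conclusion labelled as held with high confidence

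*SAP*

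**What the plan says.** Section 4 (Blinded data interpretation), Step 3, sets two triggers for 6-month mortality: "Concerning: The 85% confidence interval of the between-group difference in absolute mortality-% does not include 0.0" and "Alarming: The 95% confidence interval of the between-group difference in absolute mortality-% does not include 0.0". The same pair applies to mRS 4–6.

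A separate grade of confidence (low, moderate, high) depends only on the pooled event rate. For mortality the top grade reads "and high if the overall 6-month mortality rate was >10" per cent, and for mRS 4–6 "and high if the rate of mRS 4–6 was >15" per cent.

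In the top band of Table 3 the action for a merely concerning difference is "Notion on safety concern added to the conclusion", and the committed sentence is "Group A/B was associated with a concerningly higher mortality rate. Given the event rate, the confidence in this finding was high". The matching row of Table 4 commits to "Group A/B was associated with a concerningly higher rate of unfavorable functional outcome. Given the event rate, the confidence in this finding was high". Step 5 carries these sentences into the trial's interpretation, and the introduction to Section 4 rules out changes once the groups are unblinded. In the low and moderate bands a merely concerning difference does not reach the conclusion.

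**The concern.** The 'Alarming' trigger has its own row. The 'Concerning' row is therefore the only one to apply exactly when the 85% CI excludes zero and the 95% CI does not. In the top bands that result gets the same placement and the same confidence grade as one that passes the 95% level; only the adverb differs.

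A high pooled event rate means there are many events. It does not show that the arms differ. The committed sentence nevertheless speaks of confidence in the finding, and the finding is an excess in one arm. At stake is a published conclusion linking one arm to more death or disability, described as held with high confidence, in a trial that the SAP itself says was not powered for these outcomes.

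**Working it through.** **Inputs.** From the SAP: 289 per group (2.9.2); assumed mortality 5% and mRS 4–6 10% (Section 4, Step 3); triggers and bands as above. My assumptions: unstratified Wald intervals, since Step 3 names no interval method; equal true rates in the two arms; deaths counted within mRS 4–6; and every event rate other than 5% and 10%.

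**The plan's own figures.** The SAP text gives no error rate for the safety scheme, and Figure 4 is not shown, so there is nothing to reproduce there. The group size does reproduce: (1.960 + 0.842)² × 2 × 0.096 × 0.904 / 0.075² = 242.2, so 243 per group and 486 in total; 486/(1 − 0.157) = 576.5, so 577, made even at 578, or 289 per group.

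**What the labels do.** With d = a/289 − b/289 and SE = √[pA(1−pA)/289 + pB(1−pB)/289], the 85% CI is d ± 1.4395 SE and the 95% CI is d ± 1.9600 SE.

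| Events | Pooled rate | Difference (points) | 85% CI | 95% CI | p | Label and place |
|---|---|---|---|---|---|---|
| 37 vs 25 deaths | 10.7% | 4.15 | 0.45 to 7.85 | −0.88 to 9.19 | 0.106 | high, conclusion |
| 52 vs 38 mRS 4–6 | 15.6% | 4.84 | 0.51 to 9.18 | −1.05 to 10.74 | 0.108 | high, conclusion |
| 20 vs 6 deaths | 4.5% | 4.84 | 2.38 to 7.31 | 1.49 to 8.20 | 0.005 | low, discussion only |

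For the first row, SE = 2.568 points, so the 95% limits are 4.15 ± 1.96 × 2.568 = 4.15 ± 5.03. The third row has much the strongest evidence of a difference, yet it gets the weakest label and the less prominent place.

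**How often it would happen with no true difference.** Per endpoint, the 85% rule fires in about 15% of trials and the 95% rule in about 5%, so about 10% are concerning but not alarming. That 10% matters here only if the pooled rate also falls in the top band. The chance that pooled mRS 4–6 exceeds 15% is about 0.0001 at a true rate of 10%, and 0.25, 0.75 and 0.97 at 14%, 16% and 18%. For example, at 16%: 0.75 × about 0.10 = 0.075.

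Exact binomial enumeration for single endpoints, and multinomial simulation for the two together, give the chance of at least one 'high' conclusion sentence whose 95% CI includes zero:

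| True mortality / mRS 4–6 | Chance |
|---|---|
| 5% / 10% (planned) | well under 0.01% |
| 6% / 12% | about 0.2% |
| 5% / 16% | 7.5% |
| 5% / 18% | 9.7% |
| 12% / 20% | about 17% |

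For single endpoints, 294 and 293 per arm (the 587 randomized) give the same picture.

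**The case against.** The best defence is that the scheme has two axes and the sentence shows both. 'Concerningly' or 'alarmingly' gives the strength of the signal. Low, moderate or high gives the amount of information, tied openly to the event rate. The 85% level was fixed in advance as a sensitive harm screen, and low power is an ordinary reason to use one. Tables 5 and 6 report both intervals and the p-value. At the planned rates the top bands are almost never reached.

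Much of this stands. The 85% threshold is legitimate, the intervals are in the minutes, and the reach at planning rates is negligible. What remains is the wording. Citing the event rate shows where the label comes from, but the sentence still claims confidence in a between-group excess, and it carries no interval into the conclusion.

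A reader might infer three stronger points, which the document does not support:

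- *A contradiction with the 5% level in Section 3.2.* That section says "The statistical testing of other endpoints will also be performed using a two-sided significance level of 0.05", but the sentence before it assigns mortality and mRS 4–6 to 85% and 95% CIs. They are a declared exception.
- *A false-positive rate of 15% per endpoint for the conclusion.* This holds only once the top band is almost certain to be reached.
- *A false 'high' sentence in 22.6% of trials (12% mortality, 20% mRS 4–6).* That count includes trials that also pass the 95% level, which alone account for 8.0%. The defect described here affects about 17%; the two groups overlap because one trial can have one endpoint of each kind. Nothing in the SAP supports rates that high.

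**Conclusion.** The point holds as a wording defect in two contingency cells. In the top bands the SAP commits the authors to describe, in the conclusion and with high confidence, a difference with p between 0.05 and 0.15. Because the label ignores the interval, it can rank weaker evidence above stronger.

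Its size depends on the event rates. It is practically nil at the SAP's planning values, and ranges from about 0.2% to about 17% of null trials over the higher rates assumed above. These figures rest on Wald intervals, 289 per arm and equal true rates. No analysis and no part of the primary comparison is affected. Severity: minor.

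**What to change.** In the 'Concerning' cell of the >10% band (Table 3) and of the >15% band (Table 4), replace the committed sentence with one of this form: *a possible excess of x points (95% CI a to b, which includes 0)*. In those bands keep the word 'high' for the 'Alarming' rows only.

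The 85% screen, the bands and the placement rules stay as they are. The cost is two reworded cells, with no change to data or analysis; it should be done before the committee sees results. The change leaves event-rate grading in place in the other cells, so the 20 against 6 example would still be graded low. It removes only the claim of high confidence for a difference that the 95% CI does not separate from zero.
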